Using the latest blood pressure guidelines set forth by the 2017 ACC/AHA recommendations (Whelton et al., 2018), and the Million Hearts Initiative guidelines (Gawlik & Melnyk, 2015) a comprehensive “one-page” with supplemental visual aids will be used. The one-page will be in the format of a single page, double sided handout that covers: medications to avoid that can increase blood pressure, and self-monitoring with the American Heart Association visual aide of how to take blood pressure on the front side. The back-side will have information on: diet, smoking cessation, and physical activity. The diet section will have a visual aid from the National Heart, Lung, and Blood Institute specific to the DASH diet recommended from the 2017 ACC/AHA guideline (Whelton et al., 2018). The smoking cessation will be addressed with the National 1-800-Quit-Now number with the participant encouraged to have a separate appointment with their PCP should this be a primary focus for them. For the purpose of this study, smoking cessation assistance requires more allocated time than what is planned for each participant. The exercise section will have a visual aid from the American Heart Association about proper type of exercise and length of time to exercise. There will be a table provided for quick reference with evidenced based recommended websites and apps for the participant should they have access to the internet. These handouts are included with this submission. The one-page document is included with the submission as “My Planned Behavior for Managing my Blood Pressure.”

3. Study Design

3.1. Study design: prospective clinical trial with human participants assigned to an intervention of a one-page handout with supplemental visual aids and optional use of suggested apps and websites as an educational intervention to improve their knowledge of blood pressure management through behavior changes recommended to them.

3.2. N/A. There will be no blinding in this study.

4. Inclusion and Exclusion Criteria

4.1. Patients will be screened with an initial interview which will be conducted over the phone. The interview script is included in this submission as “UNM HTN Phone Screen for Potential Participants.” Their Walgreens medication profile will also be reviewed to verify that they are on medications for hypertension.

PROTOCOL TITLE: Evaluating the Effect of an Evidence-Based One Page with
Supplemental Visual Aids on the Knowledge and Perceptions of Blood Pressure

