Management Among Adults with Hypertension

- 4.2.** The inclusion criteria will be: adults from 18 to 75 years old, ability to self-consent, English-speaking, able to read/write English, currently prescribed at least one medication for treatment of essential primary hypertension.
- 4.3.** There will be no special populations in this study. This study will not include adults unable to consent; individuals who are not yet adults (infants, children, teenagers); pregnant women; or prisoners.
- 4.4.** Pregnant women will be excluded due to the complexity of hypertension in pregnancy, which warrants management by an OB/GYN or other specialists. Potential participants will be asked if they are pregnant or planning to become pregnant using the screening document “UNM HTN phone screen for potential patients.” Children are excluded for three reasons: 1) the writer is only certified as an NP to work with adults; 2) the focus of this study is the population at greatest risk for high blood pressure which is adults; and 3) children with high blood pressure are rarely diagnosed with essential primary hypertension, and should be managed by a specialist. We do not have the resources to provide adequate materials in Spanish or other languages commonly spoken in NM, and further research may be needed on the effect of the intervention for non-English speaking patients.

5. Number of Subjects

- 5.1.** This is a single site study and will be done at one location, Walgreens Store #6587 in Albuquerque, New Mexico. There will be 50 participants recruited.
- 5.2.** The number to be recruited will be 50.
- 5.3.** Based on statistical analysis from UNM Statistics Department, a sample size of at least 45 patients is needed. The number to be recruited at the onset will be 50 to account for attrition.

6. Study Timelines

- 6.1.**
 - Duration of individual’s participation in research: The total expected duration of participants’ active participation is less than 60 minutes. The participants will have mailed to them at the start of the study: one-page with supplemental handouts/visual aids, list of suggested apps and web sites, pre/post survey and pre/post-test with self-addressed stamped envelopes (SASE) to return their information, and a pill box.
 - Recruitment for this study will begin August-September 2020. Duration anticipated to enroll all subjects: 30 days

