 - Total duration for researchers to complete the study: Recruitment will occur through end of Sept 2020; additional follow-up phone calls will occur through

PROTOCOL TITLE: Evaluating the Effect of an Evidence-Based One Page with
Supplemental Visual Aids on the Knowledge and Perceptions of Blood Pressure
Management Among Adults with Hypertension

September-November 2020. Data analysis will occur during the month of December 2020. Manuscript preparation and submission to scholarly publications will occur shortly thereafter with the target of January 2021.

7. Study Endpoints

- 7.1.** Primary endpoint: change in participant's knowledge of blood pressure management; change in participant's perception of making lifestyle changes to manage their hypertension
- 7.2.** Describe any primary or secondary safety endpoints: N/A
- 7.3.** Describe any exploratory endpoints:
 - 1: Participants will be asked to rate the usefulness, ease of reading, and attractiveness/visual appeal of each handout they were provided.
 - 2: Participants who choose to use any apps or web sites will be asked for feedback on usefulness, ease of reading/access, and attractiveness/visual appeal for each app or web site used.
 - 3: The subset of participants who choose to use electronic resources will be compared to the subset of participants who do not to compare any differences in the primary outcome.

8. Research Setting

- 8.1.** Site or location: Walgreens Store #6587 in Albuquerque, NM.
- 8.2.** We will recruit potential subjects from Walgreens Store #6587 in Albuquerque, NM. Participants will be recruited over the phone.
- 8.3.** Research will be performed from Walgreens Store #6587 in Albuquerque, NM.
- 8.4.** Describe the composition and involvement of any community advisory board: N/A
- 8.5.** This is a partnership with UNM College of Pharmacy, Walgreens Pharmacy, and a Doctor of Nursing (DNP) student enrolled in the DNP program at Missouri State University (MSU). Per MSU policy, once the IRB is submitted and approved through UNM, the IRB approval from UNM with a summary paragraph will be submitted to MSU for record. [name], DNP candidate, will be responsible for submitting the approved UNM IRB with summary paragraph to the MSU IRB board to complete this requirement. A cede letter is included in this submission.

9. Resources Available

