12.2 Patients will be screened for eligibility for the study at Walgreens Store #6587, with pharmacists supervising the PharmD students. Screening will be conducted with the Interview Guide included in this IRB submission as "UNM HTN Prescreen for Potential Participants." Eligible potential participants will have consent forms read and given the opportunity to ask questions about the study. Participants may choose to enroll in the study at that time, or given more time to be mailed consent forms at home and decide at another time. Once the participant consents to participation, the materials will be mailed to the participant, and the participant will complete a pre-survey ("Pre-survey for UNM HTN Study") and pre-test ("Pre-test for UNM HTN Study") on blood pressure management. Participants will be provided a one-page education with supplemental visual aids on blood pressure management with education provided by PharmD students ("My Planned Behavior for Managing My Blood Pressure"). Participants will be provided a list of suggested apps and websites ("Evidence-

PROTOCOL TITLE: Evaluating the Effect of an Evidence-Based One Page with
Supplemental Visual Aids on the Knowledge and Perceptions of Blood Pressure
Management Among Adults with Hypertension

based Websites and Apps for Blood Pressure Management") that they may use if they have a smartphone and/or internet access.

After an initial teaching phone call performed by a PharmD student, a follow-up phone call will be conducted at week 4 and 8 of the participant's enrollment.

During each phone call, study personnel will use a telephone script titled "Phone Call Script for My Planned Behavior for Managing My Blood Pressure Participants" to discuss blood pressure goals, behavioral changes, and principles of blood pressure management.

At week 8, participants will either answer their questions over the phone or be reminded to complete a post-test ("Post-test for UNM HTN Study") and post-survey ("Post-survey for UNM HTN Study") and mail in using their SASE.

12.3 The information will be collected prospectively and information will be collected at the onset of enrollment, during an initial teaching phone call, during phone calls at week 4, and 8, and from mailed in pre/post-test; pre/post surveys.

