- Post-survey ("Post-survey for UNM HTN Study"): Walgreens Store #6587. The purpose of this survey is to gauge the participant's perspectives on engaging in behavioral changes after the educational intervention. The patient may return the completed test by mail, or answer the questions over the phone if they are unable to mail their responses.

13 Data Analysis

- 13.1 Descriptive statistics will be used with demographic information, and paired t-tests will be used for the pre/posttest and pre/post surveys. The UNM Statistics Department will assist with statistical analysis.
- 13.2 Power analysis completed for the paired t-tests to detect difference in pre/post tests and surveys using: one tail, moderate effect size of 0.5, alpha probability of error of 0.05, and power standard of .95 resulted in n=45 (GPower, 2019).

14 Provisions to Monitor the Data to Ensure the Safety of Subjects

N/A. This study poses minimal risk to the patient as it utilizes only non-invasive screening interventions (education; surveys; follow-up phone calls).

15 Withdrawal of Subjects

- 15.1 A patient may be withdrawn from the study should they no longer meet inclusion criteria (for example, if they become pregnant during the study). The patient may also be withdrawn if they are not following the study protocol as agreed upon at the onset of the study. Should the patient no longer be able to be contacted after three phone call attempts, they will be withdrawn from the study. Data obtained up to that point of no contact will be maintained, and used for the study analysis.
- 15.2 The completion of this study will be on the final call to gather data & final post-test and post-survey from the participant. If the patient did make a behavior change of taking blood pressure at home, we will inquire at this time. Upon completion of the study, the participant will be encouraged to continue to see their primary care physician or other medical provider for continued blood pressure management.

PROTOCOL TITLE: Evaluating the Effect of an Evidence-Based One Page with
Supplemental Visual Aids on the Knowledge and Perceptions of Blood Pressure
Management Among Adults with Hypertension

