26.2 N/A

26.3 N/A

27 Study Test Results/Incidental Findings

27.1 Individual Results will be from each participant's responses to their pre/post-test and pre/post survey, and responses to the phone script used during initial, week 4, and week 8 phone calls.

27.2 Incidental Findings: We do not anticipate any incidental findings in this study. Participants have already been diagnosed with hypertension as per the inclusion criteria of the study.

28. Sharing Study Progress or Results with Subjects

28.1 The progress of the study will be verbally shared with the participant during each follow-up phone call and during the final study visit upon the participant's request.

28.2 The results of the study will be shared with the public in the form of plain language summary of research findings when ready for publication. Participants may request a summary of the research findings at the conclusion of the study.

29 Inclusion of Vulnerable Populations

This study will not include vulnerable populations.

30 Community-Based Participatory Research - N/A

31 Research Involving American Indian/Native Populations - N/A

PROTOCOL TITLE: Evaluating the Effect of an Evidence-Based One Page with Supplemental Visual Aids on the Knowledge and Perceptions of Blood Pressure Management Among Adults with Hypertension

32 Transnational Research - N/A

33 Drugs or Devices

33.1 Drugs: The study procedures do not involve drugs. Patients in this study may take medications as part of their blood pressure treatment; however, this study does not involve any intervention for prescribing or providing medications to the participant. Patients will only receive education aimed at behavioral changes that may improve their blood pressure management. While patients may receive their medications from Walgreens as part of their usual course of care, study personnel will not prescribe, modify, or provide patient medications as part of the study intervention. The patient will be encouraged to continue their care with their primary care physician or other medical provider for management of their blood pressure and medications.

Devices: The study is not intended to study the safety of effectiveness any specific device.

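### Week-8 answers may be taken by phone by the student who taught the participant, which could push the self-reported perception endpoint in the favourable direction

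*Combined protocol and SAP*

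**What the plan says.** - **Who teaches and who calls.** Section 12.2 begins follow-up "After an initial teaching phone call performed by a PharmD student". The week-4 and week-8 calls are made by study personnel, with no further distinction, using a script that covers goals, behaviour change and management principles. Section 9.1 expects the students to stay for the whole study, and 25.1.1 lists four of them.
- **How post measures are collected.** Section 12.2: "At week 8, participants will either answer their questions over the phone or be reminded to complete a post-test" and post-survey. Section 15.2 treats the final call as the point at which the last data and post forms are gathered. Section 12.5 is narrower: it offers the phone, for each post form, only to participants who cannot post their answers back. Section 12.2 has no such condition.
- **How pre measures are collected.** Sections 6.1 and 12.2 have the pre forms mailed out with stamped return envelopes. No phone option is written for them.
- **Endpoint and analysis.** Section 7.1 names two primary measures: knowledge, and "change in participant's perception of making lifestyle changes to manage their hypertension". Section 3.2: "There will be no blinding in this study". No comparison group is described. Section 13.1: "paired t-tests will be used for the pre/posttest and pre/post surveys". Section 13.2 sizes the study with "one tail, moderate effect size of 0.5, alpha probability of error of 0.05, and power standard of .95 resulted in n=45".

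**The concern.** Perception is self-reported. A participant who tells the person who coached them, on a coaching call, how they feel about the advice may give a more agreeable answer than they would on paper. The described procedure allows this at week 8 but has no matching phone collection at baseline, so a paired difference would not cancel it. With no control arm, nothing else in the design would remove it, and 13.1 has no term for mode or collector. The expected direction for perception is the direction of the hypothesis in 1.2 and of the one-tailed calculation in 13.2. An interviewer effect could therefore be read as a benefit of the education. If the collector and mode are not recorded at the time, the effect cannot be examined afterwards.

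**Working it through.** **1. The plan's own figure.** Inputs from 13.2: one-tailed alpha 0.05, standardised paired effect 0.5, power 0.95. Power of a paired t-test is P(T > t_crit), where T is noncentral t with n-1 degrees of freedom and noncentrality d x sqrt(n).
- n=45: t_crit = 1.680, noncentrality = 0.5 x sqrt(45) = 3.354, power = 0.951.
- n=44: power = 0.947, just short of 0.95.

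So n=45 reproduces. Recruiting 50 corresponds to a 10% loss: 45 / 0.90 = 50.

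**2. The change that reaches significance.** 1.680 / sqrt(45) = 0.25 SD of change. A bias well below the planned effect of 0.5 can therefore matter.

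**3. Effect of a collector shift when there is no true change.** Neither input is in the documents; both are assumptions:
- f, the share answering by phone: 10% to 60%
- b, the favourable shift among them: 0.1 to 0.5 SD of change

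Mean bias = f x b. The rejection rate is the formula in step 1 with d = f x b, n=45 and t_crit = 1.680. It applies to one endpoint's test.

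| f | b | Mean bias (SD) | Noncentrality | False-positive rate |
|---|---|---|---|---|
| 10% | 0.1 | 0.01 | 0.067 | 5.7% |
| 10% | 0.3 | 0.03 | 0.201 | 7.4% |
| 10% | 0.5 | 0.05 | 0.335 | 9.4% |
| 20% | 0.3 | 0.06 | 0.402 | 10.6% |
| 40% | 0.5 | 0.20 | 1.342 | 37% |
| 60% | 0.5 | 0.30 | 2.012 | 63% |

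Shifting only some participants also widens the spread of the change scores, by a factor sqrt(1 + f(1-f)b²). In the last row this is sqrt(1 + 0.24 x 0.25) = 1.030, and the rate falls from 63% to 61%. In the first row it makes no visible difference.

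**4. Which part of the range applies.** If 12.5 governs, phone is a fallback and the 10% rows are the better guide. If 12.2 governs, the phone share is uncontrolled. The text does not settle which.

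**The case against.** The strongest reply is that 12.5 confines phone answers to people who cannot return the forms, and that stamped envelopes are supplied at the start. This stands as a limit on size. It does not remove the point, because 12.2 lacks the condition and phone answers still enter the primary analysis.

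Other replies that stand, in whole or in part:

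- **Same student.** A reader might infer that the teaching student will take the answers. The documents permit this but do not say it: the later calls belong to study personnel, and 12.4 speaks of the investigator on the phone. What can be shown is a missing safeguard.
- **Knowledge.** A reader might infer that both primary measures are pushed upwards. Prompting on the phone could raise a knowledge score, but someone filling in the form at home has the handouts to consult, so a live answer could score lower. The direction is uncertain.
- **Baseline.** Students take part in screening and consent (12.2, 25.1.1), so some social pressure may already exist when the pre forms are completed. It is probably weaker than on a coaching call, but the text does not show that it is absent.
- **Unseen attachments.** The phone script and the forms are named but not included. Neutral-reading instructions may be in them.
- **Handout ratings and progress talk.** A reader might extend the point to the ratings in 7.3 or to 28.1, "The progress of the study will be verbally shared with the participant during each follow-up phone call". The ratings are exploratory, have no baseline and have no stated mode or collector. Section 28.1 concerns progress on request, and the analysis is scheduled after the calls end (6.1). Neither shows a route to bias in the primary endpoint.

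**Conclusion.** The point holds as a cheap improvement. The plan allows post measures to be taken on a coaching call, possibly by the participant's own teacher, while the pre measures are collected on paper. A favourable interviewer effect could therefore enter the paired difference for perception, and the planned analysis could not remove it.

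The size is not derivable from the documents. The range of about 6% to 63% rests wholly on the assumed phone share and shift, and no single value in it should be quoted as the expected error rate. If phone is used as rarely as 12.5 suggests, a 10% share gives about 6% to 9%. It would be wrong to conclude that the perception result will be biased; the documents support only that it could be.

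**What to change.** 1. Reconcile 12.2 with 12.5 so that the same condition on phone answers appears in both.
2. State in 12.2 and 12.5 that phone answers to the post-test and post-survey are taken by a member of the existing team who did not teach or coach that participant. They are taken before any counselling on that call, with items read verbatim, no feedback given, and the first answer recorded. If the phone script already says part of this, refer to it.
3. Record mode (mail or phone) and collector for every post form, and add to 13.1 a sensitivity analysis by mode.

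**Cost.** A few protocol sentences, two data fields, and a hand-over on some week-8 calls. No staff are added beyond the existing team, and n=45 with 50 recruited is unchanged.

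**Limits.** A different caller from the same pharmacy reduces pressure from the teacher but leaves a difference between phone and mail. The sensitivity analysis will be imprecise if few use the phone: 10% of 45 is 4 or 5 people. It should be reported descriptively, since mode is not randomised.

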12.4 Initial study activities will occur from the Walgreens Store #6587 in Albuquerque, NM by phone calls: recruitment, enrollment, and initial education. The rest of the information will be gathered by follow-up phone calls at 4 and 8 week intervals, and mail-outs. The phone calls will be made from the Walgreens Pharmacy clinic in a room where the investigator has privacy for the phone calls to speak with the participant.

12.5 Describe, in chronological order, all research procedures and interventions being performed and when they are performed. Include:

- Recruitment: Walgreens Store #6587 by phone
- Screening interview: Walgreens Store #6587 by phone
- Verbal consent and enrollment: Walgreens Store #6587 by phone
- One-page educational intervention ("My Planned Behavior for Managing My Blood Pressure (One Page Handout)") with supplemental visual aids ("DASH diet," "AHA Healthy for Good," and "AHA Blood Pressure Management") will be sent to the mailing address given by the participant with a self-addressed stamp envelope in order to return pre/post-test and pre/post-survey.
- One-page educational intervention with supplemental visual aids: from Walgreens Store #6587 via mail. Education on blood pressure management will be provided to the participant by PharmD students via a phone call after enrollment once patient receives items in the mail. ("Phone call Script for My Planned Behavior for Managing My Blood Pressure Participants").
- Follow-up phone calls at 4 and 8 week intervals: Phone calls will be made to the phone number provided by the participant. Phone calls will be made from private rooms at Walgreens Store #6587. Study personnel will use a phone script ("Phone call Script for My Planned Behavior for Managing My Blood

PROTOCOL TITLE: Evaluating the Effect of an Evidence-Based One Page with Supplemental Visual Aids on the Knowledge and Perceptions of Blood Pressure Management Among Adults with Hypertension

Pressure Participants") to discuss blood pressure goals, behavioral changes, and principles of blood pressure management.

- Post-test on blood pressure management ("Post-test for UNM HTN Study"): Walgreens Store #6587. The purpose of this test is to determine the participant's knowledge of blood pressure management after the educational intervention. The patient may return the completed test by mail, or answer the questions over the phone if they are unable to mail their responses.

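### No visible passage requires either knowledge test to be answered from memory, so the primary change score can mix learning with any difference in look-up between pre-test and post-test

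*Combined protocol and SAP*

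**What the plan says.** Section 7.1 names the endpoint: "Primary endpoint: change in participant's knowledge of blood pressure management", alongside change in perception. Section 12.5 gives the post-test's purpose as determining the participant's "knowledge of blood pressure management after the educational intervention".

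On how the post-test is taken, 12.2 says "At week 8, participants will either answer their questions over the phone or be reminded to complete a post-test", with return by mail. Section 12.5 adds: "The patient may return the completed test by mail, or answer the questions over the phone if they are unable to mail their responses".

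On what participants have in hand, 6.1 says "The participants will have mailed to them at the start of the study: one-page with supplemental handouts/visual aids". The same list goes on to a set of apps and web sites and then "pre/post survey and pre/post-test with self-addressed stamped envelopes (SASE) to return their information, and a pill box". In 12.2 the pre-test is completed once the materials have been mailed after consent. Nothing says that the handouts are returned or that they stay unopened until the pre-test is done. The background (2.3) describes the handout: "The one-page will be in the format of a single page, double sided handout that covers" medications to avoid, self-monitoring, diet, smoking cessation and physical activity.

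Sections 3.1 and 3.2 describe no comparator and no blinding. Section 13.1 specifies paired t-tests, and 13.2 makes them one-tailed with alpha 0.05.

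No visible passage asks for answers from memory, sets a time limit, or records whether materials were consulted. The test forms and the phone script are separate attachments that are not shown.

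**The concern.** A knowledge score measures knowledge only if the respondent answers from memory. Here the participant fills in a form at home or answers by phone, and can have at hand a reference sheet and visual aids on the same broad subject. A correct answer may then be recalled or read off the sheet.

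With no control group, the only contrast is post-test minus pre-test within person. Whatever differs between the two occasions enters that contrast, including how many people look answers up. Analysts cannot separate the two sources afterwards, because neither the test conditions nor the use of materials is recorded. At stake is whether the first-named primary result can be reported as a change in knowledge. The perception survey is not affected in the same way.

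**Working it through.** **The plan's own figure.** Section 13.2 gives one tail, effect size 0.5, alpha 0.05, power 0.95 and n=45. I used exact power for a one-sided paired t-test, with df = n−1 and noncentrality d×√n:

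- n=44: power 0.947
- n=45: noncentrality 0.5×√45 = 3.354, power 0.951

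So n=45 reproduces. At n=45 the critical t is 1.680, and the smallest observed standardised change that reaches significance is 1.680/√45 = 0.25. The sample size is not in question; this point concerns what the score measures.

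**Assumed inputs.** The documents do not show the instruments. I assume that:

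- 80% of items can be answered from the handouts
- 60% are correct unaided and 95% when looked up
- there is no true learning
- the SD of the change score is 20 points

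Only n=45, the single tail and alpha 0.05 come from the plan.

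**Formula.** Mean gain = (share looking up at post-test − share looking up at pre-test) × 0.80 × (95 − 60) = net share × 28 points. Standardised gain d = gain/20, and the noncentrality is d×√45.

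| Net look-up (post − pre) | Gain, points | d | Noncentrality | Chance of a significant gain |
|---|---|---|---|---|
| −25% | −7 | −0.35 | −2.35 | under 0.1% |
| −10% | −2.8 | −0.14 | −0.94 | 0.5% |
| 0% | 0 | 0 | 0 | 5% |
| +10% | 2.8 | 0.14 | 0.94 | 24% |
| +25% | 7 | 0.35 | 2.35 | 75% |
| +50% | 14 | 0.70 | 4.70 | over 99% |

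With an SD of 15 or 25 points, the +10% row becomes 34% or 18%, and the +25% row becomes 92% or 58%.

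**Cross-check with a different model.** I simulated 10 items, 60% known, look-up recovering half of the unknown items, and n=45. Without learning, the results were:

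- Look-up at the post-test only, by 10%, 25% or 50% of participants: rejection 15%, 44% or 90%.
- Equal look-up at both tests (25% or 50%): no mean gain and about 5% rejection.
- 50% at pre-test and 25% at post-test: a change of −0.5 items and 0.1% rejection.

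The downward side matters too. If participants truly learn 30% of what they did not know, the gain without look-up is 1.2 items and power is 99%. With 50% looking up at the pre-test only, the gain falls to 0.2 items and power to 14%. With 50% at both tests, the gain is 0.9 items and power 83%. Equal look-up therefore cancels fully only when there is no learning, and otherwise dilutes a real gain.

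**The case against.** The strongest objection is that a reader might infer a bias in favour of the hypothesis in 1.2: a pre-test without an answer source, then a post-test with one. The documents do not support that. Section 6.1 puts the handouts and both tests in the same initial mailing, and 12.2 has the pre-test completed after the materials are mailed. The answer source can be in the house on both occasions, so the direction is not fixed. This stands, and the table is therefore written in terms of the net share. The asymmetry would become clearly upward if the baseline were moved ahead of the handouts without also controlling the post-test. Correcting baseline timing alone would therefore not settle the matter.

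Other points on that side:

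- **The forms or script may already carry the instruction.** They may. In that case 12.2 and 12.5 need only state it.
- **Overlap between test items and handouts is inferred.** True, since no item is shown. The 80% is an assumption.
- **The week-8 call covers the same principles.** What is learned on that call is part of the intervention effect, not look-up, and I do not count it as bias.
- **Phone answering leaves less room for look-up.** It does, without excluding it. Section 12.5 offers it to those unable to mail, and the mix of modes is not fixed.
- **Using a handout is the purpose of the intervention.** Finding an answer may be useful, but 7.1 and 12.5 name knowledge. If open-book performance is intended, the plan should say so.

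**Conclusion.** The point holds as a gap in test conditions. On the visible text neither knowledge test is closed-book, participants can have the handouts at both, and an uncontrolled paired t-test cannot separate learning from a difference in look-up. The bias follows post-test minus pre-test look-up and may go either way. Under the stated assumptions, a net excess of 10% at the post-test raises the chance of a significant result without learning from 5% to about 24%, and a net 25% raises it to about 75%. A net excess at the pre-test lowers it below 5% and can hide real learning. These figures rest on assumed item and look-up rates; the documents give none.

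A reader might also infer that a positive result could not be read as a change in knowledge at all. That goes too far: part of the gain could be look-up, and how much is unknown. The change is worth making before the forms go out, because it cannot be recovered in analysis. It has no bearing on n=45.

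**What to change.** In 12.2 and 12.5, and on the forms themselves:

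1. Print the same instruction on the pre-test and the post-test: answer from memory, with handouts, web sites and apps put away. Put the same sentence in the phone script, to be read before any answers are taken by phone.
2. Add one closing item to both tests asking whether the participant looked at any materials while answering. Asking only at the post-test would leave pre-test users unidentified.
3. Record whether each test was answered by mail or by phone.
4. In 13.1, keep all participants in the primary analysis, and report a sensitivity analysis that excludes anyone who reports look-up at either test.

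If the attached forms and script already contain the instruction, item 1 reduces to stating it in the protocol.

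**Cost:** one sentence on two forms and in the script, one extra item on each test, one mode field and one additional analysis. Sample size and contacts do not change. Compliance is self-reported, and the observed gain may be smaller. The sensitivity subset is selected after baseline, so it is supportive only.
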